Patients who are unable or unwilling to participate in any of the elements of prehabilitation will be excluded. These include those that have cognitive disability (including unconsciousness), cardiac or clinical instability, functional or anatomical impairment which impairs ability to participate, language barrier or patient refusal. Any language barrier will be identified by the primary clinical team and communicated to the research team. These patients will be excluded as we do not have the translating facility for the purposes of this study. Patients that have impending surgery within 72 hours of arrival to hospital will be excluded. Patients who are awaiting surgery in district hospitals or outside of Castle Hill Hospital will be excluded. A non-exhaustive list of exclusion criteria is included below.

Cardiac/ clinical instability such as:

- Recurrent unstable angina/ crescendo angina
- Untreated decompensated heart failure
- Malignant arrhythmias awaiting treatment
- Resting tachycardia (HR>100 bpm)
- Left ventricular outflow obstruction such as Aortic Stenosis with pre-syncopal or syncopal symptoms
- Unresolved acute pericarditis or myocarditis
- Second or third degree heart block without pacemaker
- Aortic Dissection
- Myxoma

Functional/ anatomical impairment such as:

- Severe musculoskeletal conditions that would prohibit exercise
- Amputees
- Registered blind

Patient recruitment and screening

Patients will be identified on admission via the acute admission board and during multi-disciplinary team (MDT) meeting. All acute patients waiting for cardiac surgery in CHH will be eligible to participate in the survey. As such, they will be approached, given information and invited to do so by a member of the research team.

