Safety of exercise has not been assessed in this group of patients. To ensure safety of participants, the interventions will be done within the cardiology and cardiac surgery department area in Castle Hill. This enables the participant to have access to round the clock medical and surgical care. The exercise will be stopped if the patient develops symptoms such as angina (chest pain, or pain radiating down the left arm), arrhythmias or any syncopal symptoms. If the symptoms do not improve with rest, they will receive appropriate medical treatment. The exercise will then be stepped down in a gradual fashion with the minimum expectation of resistance exercise only. Participants who cannot perform at least resistance only exercise will be withdrawn from the study and the surgeons will be informed.

We anticipate that the most intense intervention in this study will be the aerobic exercise. As such, it will only be performed under 1:1 direct supervision. Participants who are able to perform the aerobic exercise will only exercise until they achieve their target heart rate. If the target heart rate is exceeded, the intensity of the exercise will be reduced. If however, they are unable to achieve their target heart rate, we will reduce the intensity of the exercise to a level that is acceptable for them. At any stage of the intervention, if the patient develop symptoms as described above, the intervention will be stopped, they will be assessed and treated by the medical team in the same hospital.

We anticipate some patients with cardiac conditions may experience symptoms of postural hypotension which may impact their ability to perform the test. If this occurs, it will be documented by the assessor and patients are told to rest before trying the test again. If they are unable to perform the test at all, they will be withdrawn from the study. We will record adverse and serious adverse events.

In the event that the patient develop evidence of worsening cardiac condition either related or unrelated to the intervention, they will be assessed by the medical team and treated appropriately either with alteration of medication or possibly have the surgery expedited. The decision for treatment options lie with the medical team directly involved in the patient's care. The researchers will not influence the decision regarding the patient's treatment.

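### The Safety section gives two differing rules for exercise-induced angina, arrhythmia or syncopal symptoms, and neither says that the medical review must come before exercise restarts

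*Protocol*

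**What the plan says.** The Safety section of the Protocol opens by saying that exercise safety is untested in this group. Its first paragraph lists angina, arrhythmias and syncopal symptoms as reasons to stop exercise. It continues: "If the symptoms do not improve with rest, they will receive appropriate medical treatment". The next sentence is "The exercise will then be stepped down in a gradual fashion with the minimum expectation of resistance exercise only", followed by "Participants who cannot perform at least resistance only exercise will be withdrawn from the study and the surgeons will be informed". On the setting, the same paragraph notes: "This enables the participant to have access to round the clock medical and surgical care".

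The second paragraph deals mainly with aerobic exercise but ends with a rule that applies throughout the programme: "if the patient develop symptoms as described above, the intervention will be stopped, they will be assessed and treated by the medical team". It refers back to the symptoms in the first paragraph and sets no condition about rest.

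Under Intervention, Resistance/strength exercise, patients who cannot do aerobic exercise, with symptoms given as one example of a reason, are moved to resistance exercise alone. No medical review is mentioned there.

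The Exclusion criteria treat some forms of these symptoms as cardiac instability: "Recurrent unstable angina/ crescendo angina", "Malignant arrhythmias awaiting treatment" and "Left ventricular outflow obstruction such as Aortic Stenosis with pre-syncopal or syncopal symptoms".

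**The concern.** The same event falls under two instructions that do not match. For an episode that settles with rest, one paragraph goes from stopping to stepping down without naming a doctor, and the other sends the patient to the medical team. A member of staff who works from the first paragraph, or from the resistance-exercise text, could start the stepped-down exercise before anyone medical has seen the patient.

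The step-down also moves towards less oversight. Aerobic sessions are supervised by an exercise physiologist with an ECG or heart rate monitor attached. Resistance exercise is done at the bedside from an application or a leaflet, and no supervision is stated for it.

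At stake is whether a clinician decides, before further exertion, if a settled episode points towards the kind of instability that would have excluded the patient at entry. Rules for stopping and restarting exercise belong in the protocol and would not normally be left to a statistical analysis plan.

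**Working it through.** There is no planned figure to reproduce and no test or sample size involved. The check sets the relevant texts side by side for one case: a participant has angina, an arrhythmia or a syncopal symptom during exercise, and it settles with rest.

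| Source in the Protocol | Trigger | Medical review stated if symptoms settle? | Review required before exercise restarts? |
|---|---|---|---|
| Safety, paragraph 1 | The named symptoms | No; treatment only if rest fails | Not stated |
| Safety, paragraph 2 | The same symptoms, by back-reference | Yes | Not stated; restart is not mentioned |
| Safety, paragraph 4 | Evidence of a worsening cardiac condition | Only if the episode is taken as such evidence | Not stated |
| Intervention, Resistance/strength exercise | Unable to do aerobic exercise, for example because of symptoms | No | Not stated |

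**Step 1: is it the same event?** Yes. Paragraph 2 takes its symptoms from paragraph 1, so the two rules overlap fully on the trigger.

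**Step 2: do the rules differ?** Yes. Paragraph 1 attaches a rest condition to treatment and is silent on assessment. Paragraph 2 has assessment and treatment with no condition.

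**Step 3: what does the step-down follow?** The step-down sentence in paragraph 1 can be read as following the stop or as following medical treatment. On the first reading, a settled episode leads to stepped-down exercise with no review stated. On the second, paragraph 1 gives no next step at all for a settled episode. Neither reading supplies a review before restart.

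**Step 4: does another provision supply the order?**
- Round-the-clock care is access to help; it does not trigger a review.
- The diary, staff notes and documentation of cardiac symptoms (Baseline data collection; Outcome measures) are records.
- Withdrawal by the clinician (Outcome measures) depends on a change in circumstances that affects completion.
- Paragraph 3 of Safety concerns postural hypotension during the tests, where the patient rests and tries again.
- Informing the surgeons is tied in paragraph 1 to withdrawal.

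None of these makes a settled episode a reason for review before exercise resumes.

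**Step 5: extra workload from a single rule.** Reviews stated per settled episode are 0 under paragraph 1 and 1 under paragraph 2. A single rule requiring review gives 1. The added reviews are therefore 1 − 0 = 1 per episode against paragraph 1, and 1 − 1 = 0 against paragraph 2.

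**The case against.** The best reply is that paragraph 2 governs. It applies at any stage of the intervention, so it covers resistance exercise too, and it has no rest condition. Paragraph 1's condition attaches to treatment and does not waive assessment, so applying the stricter rule reconciles the two. The order of words in paragraph 2, stopping and then assessment and treatment, suggests that the review follows at once and so comes before any restart. Staff delivering aerobic exercise work 1:1 with monitoring, the physiotherapy team tailors the resistance programme, and the Discussion describes these inpatients as well monitored. New exertional symptoms might also count as a worsening cardiac condition under paragraph 4.

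Most of this stands. It makes an unreviewed restart less likely and limits the point to an inconsistency with a missing order of steps. It does not remove the point. The order has to be inferred, the looser paragraph comes first, and the Intervention text repeats the move to resistance exercise without any review.

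Two stronger readings are tempting, and the Protocol supports neither:
- A reader might infer that it permits exercise to restart without medical review. It does not, because paragraph 2 requires the review.
- A reader might infer that a settled episode already meets an exclusion criterion, since each named symptom resembles a listed one. The criteria concern recurrent or crescendo angina, malignant arrhythmias awaiting treatment, and outflow obstruction with syncopal or pre-syncopal symptoms. One settled episode is not by itself any of these, and the resemblance is no evidence of how often it would prove to be.

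**Conclusion.** The point holds as an inconsistency between two safety rules. The Protocol requires medical review for these symptoms in one paragraph, omits it for settled episodes in another, and nowhere states that it must come before exercise restarts. It is worth correcting because the Protocol itself says exercise safety is untested in this group, and because the step-down leads to bedside exercise with no stated supervision.

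No numerical size can be given. The expected number of settled episodes is not stated, and for a sample of 20 the number of participants affected could be anything from 0 to 20. A reader might look for a consequence for retention, adherence or the reported safety results. Nothing in the Protocol allows one to be derived, and none is claimed.

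The conclusion assumes that the paragraphs are read as written, without an unpublished working procedure that already fixes the order. This is a change for the sponsor to consider.

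**What to change.** Align the first paragraph of Safety, and the step-down for symptoms under Resistance/strength exercise, with the second paragraph of Safety:

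1. For angina, arrhythmia or any syncopal symptom, the session stops.
2. The medical team assesses the patient, even if the symptoms settle with rest, and treats as needed.
3. Exercise at any level, including bedside resistance exercise, resumes only after that assessment, stepped down where appropriate.
4. As now, a participant who cannot manage resistance-only exercise is withdrawn and the surgeons are informed.

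The cost is a wording amendment in two places, a short delay to exercise after an episode, and one medical review per episode, which the second paragraph already requires. Sample size, outcomes and analysis are unchanged.

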All study participants will be given a booklet containing psychoeducation information. The booklet aims to explain the emotions they may feel whilst being in hospital, symptoms of anxiety, suggest how to manage anxiety, behavioural strategies that may help and signposting if they require further support. In addition to this, the participants will be given access to audio on guided meditation and relaxation. Both the booklet and audio are designed with input from in-house clinical psychologist.

Patients will be asked to score themselves on CAQ and EQ-5D-5L on day 0 and on day 7 or day before surgery. During the second assessment of CAQ and EQ-5D-5L, patients will be asked if they have read or used either the psychoeducation booklet or audio. Hospital staff will be alerted of participants that score highly and considered high risk. In addition, they will be referred to the clinical psychologist or in-hospital psychiatry liaison team.

Additional information collection

All participants will be given a diary. They will be requested to record number of times they performed unsupervised exercise, and for how long. They are also asked to document their food intake. The diary is also used as a mood monitor. Participants are encouraged to write down how they felt, if they used the recommended technique and any benefit they may experience.

Participants will be interviewed for a feedback on the prehabilitation program. The questions will centre around their opinion of the intervention in terms of acceptability, enjoyment, usefulness, accessibility and achievability. We will be gauging their reception to the exercise, psychoeducation booklet as well as mindfulness audio.

Patient and public involvement

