We will be sending out questionnaires pertaining to the patient's mental health. Patient's that score highly or show any features of mental health problem that could impact their safety will either be asked to self refer for help or be contacted by a clinical psychologist. The intervention offered will depend on the severity of condition.

Outcome measures

The primary outcome is the feasibility and acceptability of the multimodal program. Feedback will be obtained from the patient regarding the acceptability, achievability and general interest in the program.

Feasibility will be assessed by determining the number of eligible patients, participants recruited, participated and retained at the end of the intervention, the proportion of intervention sessions delivered and fidelity of delivery. Moreover, participant recruitment, retention and adherence to the intervention will be measured, as well as any adverse events.

To determine the acceptability of the intervention and to explore barriers and enablers to the implementation of the intervention, interviews will be conducted amongst participants, and staff involved in referral and intervention delivery.

Secondary objectives:

- To identify a signal of efficacy for positive changes in physical health exercise, mental wellbeing, and quality of life (using tools described);
- To identify differences in length of hospital stay, complications and readmission rates to hospital following surgery compared to usual care (based on previously collected data);
- Indications of safety concerns with prehabilitation in acute inpatient population. This is based on reported adverse events

The 6 minute walk test, hand grip, quality of life measure, spirometry and cardiac anxiety score will be measured at three points, before the intervention, day 7 and day 14 or before the surgery. If the surgery happens before day 7, there will only be two measurements. Information on any cardiac symptoms and their association with the exercise will be documented.

The end of the trial is defined as the day of surgery for the last participant. Participants may choose to withdraw at any point of the trial. If they are changes in circumstances which would impact their ability to complete the trial, they will be withdrawn by the clinician.

Statistical method

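### The protocol removes from the study, and not only from exercise, participants who cannot manage resistance exercise, so their remaining pre-surgery EQ-5D-5L and CAQ can be lost

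*Protocol*

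**What the plan says.** The Safety section of the protocol uses two kinds of wording. Where symptoms appear during a session, only the activity ends: "At any stage of the intervention, if the patient develop symptoms as described above, the intervention will be stopped". Exercise is then stepped down, with resistance work as the minimum. For those who cannot reach that minimum the consequence is larger: "Participants who cannot perform at least resistance only exercise will be withdrawn from the study and the surgeons will be informed".

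Two other withdrawal rules sit nearby. In the paragraph on postural hypotension: "If they are unable to perform the test at all, they will be withdrawn from the study". Under Outcome measures: "If they are changes in circumstances which would impact their ability to complete the trial, they will be withdrawn by the clinician". None of the three says what is still collected afterwards.

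Data that need no exercise are planned as follows.

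- Under Worry: "Patients will be asked to score themselves on CAQ and EQ-5D-5L on day 0 and on day 7 or day before surgery". Outcome measures instead schedules these scores at three points: before the intervention, at day 7, and at day 14 or before surgery.
- Under Additional information collection: "Participants will be interviewed for a feedback on the prehabilitation program".
- Under Outcome measures: "The primary outcome is the feasibility and acceptability of the multimodal program", followed by "Feedback will be obtained from the patient regarding the acceptability, achievability and general interest in the program".

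The Statistical method section takes improvement in the 6-minute walk test, hand grip, EQ-5D-5L and CAQ as a sign of possible efficacy. The trial has one arm of 20 patients.

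**The concern.** The trigger for withdrawal is inability to exercise, yet the questionnaires and the interview can be completed by someone who does no exercise at all. A ward researcher who follows the Safety section literally would have no instruction to return to a withdrawn participant with the EQ-5D-5L and CAQ before surgery. A score not asked for then cannot be recovered from records, and no analysis plan can repair that.

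The loss would not be random. It would fall on participants who tolerated the programme least, in a population where the protocol itself says the safety of exercise has not been assessed. With no control arm, nothing offsets a mean change computed only on those who stayed. The same people's views matter for acceptability, which is part of the primary outcome.

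**Working it through.** The plan gives no figure to reproduce: no withdrawal rate, no allowance for dropout, and no threshold for improvement. The check is therefore a reading of the text, followed by an illustration of scale.

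**Text, item by item: what happens after withdrawal under the resistance-exercise rule?**

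- *Remaining EQ-5D-5L and CAQ.* No section provides for them. On the Worry schedule, a participant withdrawn after day 7 already has the second score, so the exposure is mainly early withdrawals. On the three-point schedule in Outcome measures, the last score is exposed as well.
- *Feedback interview.* Additional information collection and Outcome measures speak of participants without limiting this to completers, and Patient recruitment and screening asks permission for contact after the study. The interview is at risk but has a route.
- *Adverse events.* Safety says they will be recorded and gives no end at withdrawal.
- *Length of stay and complications.* Setting says admission data are collected routinely for all cardiac surgery patients, and surgery takes place in the same hospital. Little loss is expected if those records are used. Readmission is not named among the routine data.

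**Scale for the questionnaire scores.** Inputs: n = 20 (Abstract); d = 1 to 4 withdrawn without a second score (assumed); correlation ρ between tolerance and score change (assumed 0, 0.5 or 1); no true effect. Changes are in SD units, oriented so that higher is better.

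The d participants with the lowest tolerance are dropped and the mean change of the other 20 − d is taken. With jointly normal tolerance and change, the expected mean is

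bias = ρ × m(d),

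where m(d) is the expected mean of the 20 − d highest of 20 standard normal values. The standard error is about 1/√(20 − d). Simulation with 200,000 runs for each ρ gives:

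| d | m(d), bias at ρ = 1 | bias at ρ = 0.5 | bias at ρ = 0 | SE | bias/SE at ρ = 0.5 |
|---|---|---|---|---|---|
| 1 | 0.098 | 0.049 | 0 | 0.229 | 0.21 |
| 2 | 0.181 | 0.091 | 0 | 0.236 | 0.39 |
| 3 | 0.259 | 0.130 | 0 | 0.243 | 0.53 |
| 4 | 0.332 | 0.166 | 0 | 0.250 | 0.67 |

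For example, with d = 4 and ρ = 0.5 the bias is 0.5 × 0.332 = 0.166 SD, and 0.166/0.250 is about 0.67 standard errors. The column for ρ = 1 is an upper bound under this model.

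**The case against.** The strongest reply is that the harm is inferred from what the protocol does not say. No section states that data collection ends at withdrawal, and the information sheet or consent form, which are not at hand, may cover it. Withdrawals stay visible in the retention count. The resistance-exercise trigger may be uncommon, because unstable and functionally impaired patients are excluded and the exercise is individualised. Some very unwell patients may have surgery expedited and miss a questionnaire under any rule. At ρ = 0.5 the bias stays below one standard error.

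Much of this stands, and it limits the size. It does not remove the point. The Safety section states a rule, that these participants leave the study, and sets it beside other sentences in which only the activity stops. A retention count shows that someone left; it does not supply their scores.

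Four stronger readings are tempting, and the documents do not support them.

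- *That an acceptability percentage would be inflated.* The Statistical method section analyses acceptability qualitatively and defines no proportion. A lost interview loses content; it does not shift an endpoint by a calculable amount. Staff who deliver the intervention are interviewed too.
- *That complications, stay and adverse events are lost.* Their collection is not limited to completers, and routine records exist for stay and complications.
- *That the rule on the unnamed test removes the least tolerant.* That rule is tied to postural hypotension. It may concern the baseline test mentioned under Setting, which comes before any intervention, so there would be no programme experience or change score to lose.
- *That a false-positive rate can be given.* This would need a rule for what counts as improvement, and the protocol states none.

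**Conclusion.** The point holds for the resistance-exercise rule. As written, that rule can end questionnaire collection for participants who tolerated the programme worst, and it makes their interviews uncertain. The firm part is the remaining pre-surgery EQ-5D-5L and CAQ, mainly for those withdrawn before the day-7 or pre-surgery assessment.

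The size cannot be known from the protocol. As an illustration, 1 to 4 withdrawals out of 20 would shift the mean change by 0.05 to 0.17 SD in the favourable direction at an assumed correlation of 0.5, and by nothing if tolerance and score change are unrelated. This assumes that those withdrawn are exactly the least tolerant and that none gave a second score. The effect is modest beside the sampling error of a 20-patient pilot, but it is avoidable at little cost. It should be corrected. Confidence is medium, because consent documents not at hand may already provide for data after withdrawal.

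**What to change.** Leave all clinical rules on when exercise or any other component stops as they are. In Safety and Outcome measures, separate stopping the intervention from ending data collection. State that, unless consent is withdrawn, a participant who stops:

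- still completes the remaining EQ-5D-5L and CAQ before surgery;
- is offered the feedback interview;
- is followed for adverse events; and
- is followed for length of stay, complications and readmission, from records where these exist.

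As a secondary clarification, state which test, at which visit, is meant in the postural-hypotension paragraph of Safety.

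The cost is protocol wording, plus a few extra questionnaires and interviews with inpatients in the same hospital. No new procedure is needed.

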Patients that are unable to use the exercise bikes will be asked to walk or use the arm crank as an alternative exercise. Both these activities will be tailored to the individual ability.

Regardless of the type of aerobic exercise, the aim would be to achieve a target heart rate for each patient (40%-50% heart rate reserve). During the exercise, their heart rate will be recorded every minute alongside the corresponding exercise wattage. RPE will be recorded at the end of each session.

Resistance/ strength exercise

Patients will be given the option of an in hospital application (Physiotech) or pictorial and written information on how to perform resistance exercise by their bedside. The physiotech application is currently in use by the hospital physiotherapy team for other surgeries such as orthopaedic. However, this application has not been used in cardiac surgery. The physiotherapy team will be tailoring the exercise for the patients and setting the appropriate recommended targets. The application will require basic data on age, weight and height. The exercises will be using single-use resistance bands. Participants are encouraged to perform the exercise as often as possible with the aim of achieving at least 2 session per week.

Patients who are unable to perform the aerobic exercise (eg due to physical limitation or symptoms) will be asked to perform resistance exercise only. The frequency of exercise will be individualised according to patient's ability and fitness level.

Inspiratory muscle training

Patients at high risk of respiratory complications are given spiroball after the surgery for inspiratory muscle training. As part of the prehabilitation, patients will be given spiroball before the surgery and taught how to use it. The importance of inspiratory muscle training will be explained. Patient can access spiroball training on the physiotech application. The target will be for patients to do 3 sets (consisting of 6 breath each), 5 times a day. Preoperative training should also aid better post operative compliance.

Worry

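### Postural hypotension symptoms in the test lead to rest and retry, or to withdrawal, while the symptom stop rule is worded only for exercise and the intervention

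*Protocol*

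**What the plan says.** The protocol's Safety section holds two sets of rules for symptoms.

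**During exercise.** Exercise stops "if the patient develops symptoms such as angina (chest pain, or pain radiating down the left arm), arrhythmias or any syncopal symptoms". If rest does not settle the symptoms, medical treatment follows. Exercise is then stepped down, with resistance work alone as the floor, and only a participant who cannot manage that floor is withdrawn. The next paragraph, on supervised aerobic work, adds that when such symptoms occur at any stage of the intervention, "the intervention will be stopped, they will be assessed and treated by the medical team in the same hospital". The section on resistance/strength exercise agrees: "Patients who are unable to perform the aerobic exercise (eg due to physical limitation or symptoms) will be asked to perform resistance exercise only".

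**During the test.** The third paragraph of Safety expects that some patients will have symptoms of postural hypotension that affect their performance of a test it does not name. The instruction is: "If this occurs, it will be documented by the assessor and patients are told to rest before trying the test again". It continues: "If they are unable to perform the test at all, they will be withdrawn from the study".

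Under Setting, the baseline test follows consent and the intervention starts after it. Under Outcome measures, feasibility is judged partly by the number of "participants recruited, participated and retained at the end of the intervention".

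**The concern.** There are two separate issues in the same short paragraph.

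The first is safety wording. These are acute inpatients awaiting cardiac surgery, and the protocol itself says that the safety of exercise has not been assessed in this group. Light-headedness on standing or walking may be hard to tell from an early syncopal symptom. In an exercise session a syncopal symptom means stopping and being assessed by the medical team. In a test, an assessor who follows the paragraph literally records the symptom, lets the patient rest and repeats the test. No clinical check is stated before the repeat.

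The second is the consequence of failing the test. Withdrawal from the study follows from being unable to complete what is, for the walk test, spirometry and grip strength alike, a secondary measurement. The exercise rules keep a participant with symptoms in the study as long as resistance exercise is possible. A participant able to receive the programme could thus be lost, and the loss would count against retention, which is part of the primary outcome.

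**Working it through.** No calculation tests this point, and the protocol gives no figure to reproduce. The check is a comparison of the relevant text.

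**Step 1: which test?** The Safety paragraph does not say. Baseline data collection lists three physical measurements: the six-minute walk, spirometry and hand grip. Postural symptoms are most likely to matter in the walk, so that is the natural reading, but it remains a reading.

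**Step 2: does the stop rule reach the tests?** Its first statement governs exercise. Its second governs the intervention and sits in the paragraph on aerobic work. Setting places the baseline test before the intervention, so on the wording the baseline test is outside both. The later tests (day 7, and day 14 or before surgery) fall within the intervention period, so the phrase about any stage of the intervention could be stretched to them. Even then, what it orders stopped is the intervention, not the test. The gap is clearest at baseline.

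**Step 3: compare the handling.**

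| | Exercise session | Test |
|---|---|---|
| Symptoms named | Angina, arrhythmia, syncopal symptoms | Postural hypotension |
| First step | Stop, rest | Document, rest |
| Next step | Assessment and treatment by the medical team; step down | Try again |
| Check stated before resuming | Medical assessment | None |
| Monitoring stated | ECG/heart rate monitor and supervision (aerobic work) | None |
| Withdrawn when | Resistance exercise alone is not possible | The test cannot be done at all |

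Both routes begin with rest. They differ in the second step and in the withdrawal criterion. No other section states a clinical check before a test is repeated.

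**Step 4: follow one participant.** Suppose the test is the walk, and someone cannot do it because of postural symptoms but can use resistance bands at the bedside. The exercise rules keep that person in the study on resistance exercise only. The test rule withdraws the same person. Nothing in the resistance section makes a completed walk test a condition of receiving that exercise.

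**Step 5: effect on the outcome.** Retention at the end of the intervention is a feasibility measure. A withdrawal for an undone secondary measurement lowers it for a reason unrelated to whether the programme can be delivered. How often this would happen cannot be derived, because the protocol says only that some patients may have the symptom.

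**The case against.** **The missing check is bedside detail.** The paragraph misstates nothing, the exercise rule also starts with rest, and ward staff would ordinarily take a pulse and blood pressure. This has some force. It does not remove the difference in the second step: the protocol wrote medical assessment into one rule and an unconditional retry into the other.

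**Other safeguards reach the tests.** A reader might infer that the tests are done without protection. The documents do not support that. Under Setting, assessments take place on the cardiac surgery and cardiology ward. Safety provides for medical and surgical care at all hours in the area where the interventions are done. The exclusions remove several unstable groups, among them "Left ventricular outflow obstruction such as Aortic Stenosis with pre-syncopal or syncopal symptoms". Safety also has a general clause, "In the event that the patient develop evidence of worsening cardiac condition either related or unrelated to the intervention", which leads to medical assessment and is not confined to exercise. Adverse events are recorded. All of this stands and limits the risk considerably. What it leaves open is narrow: the exclusions act before entry, event recording comes afterwards, and the general clause needs evidence of worsening and puts no condition on a retry.

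**The two withdrawal rules do not truly conflict.** A reader might infer a flat contradiction. That goes too far. It depends on reading the unnamed test as the walk. The test rule applies only to someone who cannot perform it at all, after rest and a further attempt, so it will bite mainly at baseline. Withdrawing a patient too symptomatic to be tested is a cautious choice that can be defended, and Outcome measures separately allows withdrawal by the clinician. What survives is that the test rule is stricter than the exercise rule, and that the protocol gives no reason for tying continued participation to a secondary measurement.

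**Conclusion.** The point holds as a modest clarification of one paragraph. The symptom stop rule does not expressly cover the tests, the rule that does cover them states no check before a retry, and failure of the test leads to withdrawal where the exercise rules would keep the participant on resistance work.

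It rests on two readings: that the test is most naturally the six-minute walk, and that postural symptoms can overlap with syncopal ones. The first matters only for the withdrawal comparison. The wording gap exists whichever physical test is meant.

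No size can be attached. A reader might multiply out the schedule: two measurement points if surgery comes before day 7, otherwise three, so 20 × 2 = 40 to 20 × 3 = 60 test occasions. That only counts planned assessments and measures no risk. A reader might also infer a retention loss of 1/20 = 5 percentage points per withdrawal. That assumes that all 20 planned participants form the denominator, including anyone withdrawn before a first session, which the protocol does not settle, and no event rate is given to multiply it by. The point affects no power or sample size figure.

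**What to change.** Reword the third paragraph of the Safety section.

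1. Name the test, and extend the existing stop rule (angina, arrhythmia, syncopal symptoms) to all the physical tests, including those at baseline.
2. Allow a retry only once symptoms have settled and a heart rate and blood pressure check is satisfactory. Otherwise the medical team assesses the patient first. Medical agreement before every retry is not needed when symptoms settle and the check is satisfactory.
3. Treat a test that cannot be performed, or that is withheld, as a missed measurement. Withdraw only participants who cannot do at least resistance exercise, or whom the clinician withdraws.

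The cost is a few sentences and a brief ward check when symptoms occur. The downside is an occasional delayed or missed secondary measurement, so the before-and-after comparison for that test may rest on slightly fewer participants.
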